5.4.4. Long-term Survival for EFS

To evaluate long-term survival for EFS the proportion of subjects with EFS at 2 and 3 years will be analyzed using a 2-sided chi-square test at the 10% level of significance. This will be done for IRC and investigator assessed EFS.

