9.1.4. Posttreatment Phase (Follow-Up)

After the completion of the End-of-Treatment procedures, all subjects will enter a Posttreatment Phase. During the Posttreatment Phase, subjects randomized to ibrutinib having a response of PR or better after 3 cycles of combination treatment will continue on ibrutinib monotherapy at the same daily dose for three 28-day cycles or until disease progression or unacceptable toxicity, or up until initiating subsequent antilymphoma therapy or a conditioning regimen for stem cell transplantation, whichever occurs first.

For subjects who enter the Posttreatment Phase without disease progression, follow-up visits to assess disease progression will be completed as per [Table 3](#) and [Table 4](#) until PD, the clinical cutoff for the primary endpoint, or for up to 3 years after the date of Cycle 1 Day 1, whichever occurs first. After that, evaluations may be performed as clinically indicated at the discretion of the investigator. After the last protocol efficacy assessment at 3 years, subjects without PD will be followed for survival status as per the standard routine of care of the investigator site. If PD is assessed after 3 years, the date and reason for progression will be entered in the CRF. Additionally, if the investigator becomes aware of the subject death, the date of death will be entered in the CRF.

The interval between follow-up visits should be maintained as outlined in the Times and Events Schedules ([Table 3](#) and [Table 4](#)); if a visit occurs earlier or later than the scheduled visit date, then the next visit date should be rescheduled to maintain the required interval from the previous

visit. At any visit, if there is clinical evidence or suspicion of PD, then appropriate testing must be performed to document progression (See Section 9.2.1).

Investigators may re-contact the subject to obtain long-term follow-up information regarding the subject's safety or survival status as noted in the ICF (refer to Section 16.2.3, Informed Consent and Assent Form). Survival follow-up (physician visit or telephone contact) will be required every 4 weeks for all subjects following PD until death or study end, whichever occurs first. The interval between post-PD survival follow-up visits should be maintained at 4 weeks; if a visit occurs earlier or later than the scheduled visit date, then the next visit date should be rescheduled to maintain the required interval from the previous visit.

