9.1.5. Clinical Cutoffs

Two clinical cutoffs are planned. The first clinical cutoff will occur when approximately 30 EFS events have been observed in Part 2 of the study. The second clinical cutoff will occur when approximately 60 EFS events have been observed in Part 2 of the study. The interim analysis and final analysis of the primary endpoint EFS will take place at these 2 clinical cutoffs, respectively.

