11.3.2. Secondary Endpoints

Secondary endpoints in Part 1 (Section 2.1.1) will be provided as listings. In Part 2, tumor volume reduction at Day 14, ORR, time to response, duration of response, overall survival, and number (%) of subjects who proceed to stem cell transplantation will be summarized. Other secondary endpoints will be provided as listings.

Overall survival is defined as the duration from the date of enrollment (in Part 1) or randomization (in Part 2) to the date of the subject's death. Overall survival will be analyzed using the non-stratified log-rank test for treatment comparison in Part 2. The overall survival distribution and median overall survival with its 90% confidence interval will be estimated using the Kaplan-Meier product-limit method. The hazard ratio for ibrutinib+CIT relative to CIT alone and its associated 90% confidence interval will be calculated based on the non-stratified Cox proportional hazards model. Exploratory analysis using the Cox proportional hazards model with and without the covariates, as well as exploratory analysis on the effect of subsequent antilymphoma therapy on overall survival, will be performed as appropriate.

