11.9. Interim Analysis

During Part 2, an independent DMC will be used for ongoing, real-time review of safety and will conduct an interim analysis. The pre-planned interim analysis will be conducted when approximately 30 EFS events are reached. An independent DMC will determine the appropriateness for early stopping using the nonbinding stopping rules (Table 11) as well as other efficacy and safety endpoints. The 1-sided p-value required for early stopping for futility is ≥ 0.367 and efficacy is ≤ 0.006 if there are 30 EFS events at the interim analysis. This design employs the sequential testing approach as described by O'Brien and Fleming (1979)²⁷ to preserve the Type-I error rate. The interim analysis will also include a pharmacokinetic assessment using the available data at the time.

Table 11: Stopping Boundaries (N=72 subjects, 2 Analyses)

Analysis Number	EFS events	Approximate Time	Number of Subjects	Cumulative Error		Stopping Boundary		Observed Hazard Ratio	
				Alpha	Beta	p-value (1-sided)		Efficacy	Futility
				Efficacy	Futility	Efficacy	Futility	Efficacy	Futility
Interim	30 (50%)	32 months	46	0.006	0.07	≤ 0.006	≥ 0.367	<0.378	≥ 0.878
Final	60 (100%)	50 months	72	0.050	0.2	≤ 0.048	-----	<0.632	-----

EFS=event-free survival.

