5. EFFICACY

Analysis of efficacy endpoints will be conducted on the ITT population. [Table 3](#) summarizes the efficacy endpoints and analysis methods to be performed.

Table 3: Summary of Efficacy Analyses to be Performed

Endpoint	Analysis	Analysis Method	Population
Primary			
Event-free Survival (EFS) as assessed by IRC	Primary	Non-stratified log-rank test, non-stratified Cox regression model, all PD and death considered as events regardless of subsequent antilymphoma therapy or a conditioning regimen for stem cell transplantation. EFS is defined as the time interval from randomization to death, disease progression, or lack of CR or PR after 3 cycles of treatment.	ITT
	Sensitivity	
 1) Alternative censoring rule 1: subjects who received subsequent antilymphoma therapy or a conditioning regimen for cell transplantation are considered to have had an EFS event at the initiation of subsequent therapy 2) Alternative censoring rule 2: subjects who received subsequent antilymphoma therapy or a conditioning regimen for cell transplantation are censored at the last disease assessment showing no evidence of PD before the use of subsequent therapy 3) Alternative censoring rule 3: subjects will be censored at the last disease assessment if they progress, die or have not responded after missing ≥ 2 planned disease assessment visits. 4) Investigator assessed EFS by non-stratified log-rank test and non-stratified Cox regression model; concordance rate between the IRC-determined EFS and investigator-determined EFS 	ITT
	Subgroup	Non-stratified Cox regression model within each subgroup	ITT
Secondary			
Long-term survival (EFS) at 2 and 3 years		IRC assessed chi-square test for 2 and 3 year EFS rate.	ITT
Overall Survival	Primary	Non-stratified log-rank test, non-stratified Cox regression model, as the time interval from enrollment (Part 1) or randomization (Part 2) to all deaths considered as events regardless of subsequent antilymphoma therapy or a conditioning regimen for stem cell transplantation.	ITT
	Sensitivity	Censored at subsequent antilymphoma therapy or a conditioning regimen for stem cell transplantation.	
Overall Response in Part 1	Subgroup	Non-stratified Cox regression model within each subgroup Listing of IRC and investigator assessments for those subjects who respond.	ITT Enrolled subjects

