5.3.1. General Analysis Considerations

Descriptive statistics and subject listings will be used to summarize the data. For continuous variables, the number of observations, means, standard deviations, medians, and ranges will be used. For discrete variables, frequency will be provided. For time-to-event variables, Kaplan-Meier estimates will be provided.

Comparisons between the 2 treatment arms in Part 2 will be performed as follows: for the continuous variables representing change from baseline to a particular postbaseline timepoint, analysis of variance will be used. For discrete variables, Chi-square test will be used. For time-to-event variables, non-stratified log-rank test and non-stratified Cox proportion hazard model will be used unless specified otherwise. All tests will be conducted at 2-sided test at the 10% level of significance and 90% confidence intervals will be provided, unless otherwise stated.

Unless otherwise specified, disease progression and disease response will be based on assessments from an IRC, according to principles adapted from the International Pediatric NHL Response Criteria (Sandlund 2015).² Disease response will be evaluated by radiological imaging, physical examination, or other procedures as necessary, including but not limited to review of hematology, clinical chemistry, and lumbar puncture results. Criteria for response categories, as well as the process and convention of the IRC are detailed in a separate IRC charter.

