5.4.2. Primary Analysis Methods for EFS

Subjects who continue to respond after 3 cycles of treatment, are progression free and alive will be censored at the date of last disease assessment. Subjects with no baseline or any post-baseline disease assessment will be censored at the date of randomization.

The analysis of the primary endpoint (EFS) will be based on the ITT population. For the primary efficacy analysis, EFS will be compared between treatment groups using a non-stratified log-rank test. The Kaplan-Meier method will be used to estimate the distribution functions of EFS for each treatment group. The number of events, subjects censored, the estimate of medians, and 90% confidence interval for the medians will be presented. The plot of EFS using the Kaplan-Meier method will be presented. The estimate of the hazard ratio between the 2 treatment groups and its associated 90% confidence interval will be computed based on the non-stratified Cox proportional hazards model.

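### SAP 5.4.4 compares 2- and 3-year EFS by a chi-square test on crude proportions, although event-free subjects can be censored before those times

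*SAP*

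**What the plan says.** SAP 5.4.4 states that "the proportion of subjects with EFS at 2 and 3 years will be analyzed using a 2-sided chi-square test" at the 10% level, for IRC and investigator EFS. SAP Table 3 gives the method as "IRC assessed chi-square test for 2 and 3 year EFS rate" with ITT as the population.

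Under SAP 5.4.2, responders who "are progression free and alive will be censored at the date of last disease assessment". Subjects lacking assessments are censored at randomization. Under Protocol 9.1.4, efficacy visits run to PD, "the clinical cutoff for the primary endpoint, or for up to 3 years after the date of Cycle 1 Day 1", whichever is first. That cutoff is set by events and not by a minimum follow-up: "The second clinical cutoff will occur when approximately 60 EFS events have been observed in Part 2 of the study" (Protocol 9.1.5). Enrollment has since stopped at 31 events (Protocol 11.9.1), and follow-up lasts only as long as the sponsor keeps the study open (Protocol 17.9.1).

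Elsewhere, SAP 5.3.1 says "For time-to-event variables, Kaplan-Meier estimates will be provided". Protocol 11.3.2 does not name this endpoint among those to be summarized and adds "Other secondary endpoints will be provided as listings".

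**The concern.** A chi-square test on the full ITT set requires each subject to be classed as event-free or not at 24 and 36 months. A subject censored event-free before the landmark has no such status, and the SAP does not supply one. The missing-data rules in SAP 2.7 and 5.3 deal with dates, and the rule that missing means non-responder (SAP 5.5.3) applies to ORR only.

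Three conventions are possible: count the subject as a failure, drop the subject, or count the subject as event-free. None estimates the EFS rate. The first two are too low, because events are kept from subjects with short follow-up while their event-free counterparts are lost. The third is too high.

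At stake is a listed secondary endpoint on long-term disease control. Its reported rates would depend on a choice that could be made after the data are seen, and they could conflict with the Kaplan-Meier curve in the same report.

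**Working it through.** **1. The plan's own figures.** With 60 events, 2:1 allocation, HR 0.5 and one-sided alpha 0.05, z = √(60 × 2/9) × ln 2 − 1.645 = 2.531 − 1.645 = 0.886, so power is 81.2% (stated: at least 80%). Accrual takes 72/1.44 = 50 months. Exponential EFS with medians 10 and 5 months gives 30.3 events in 46 subjects at month 32 (stated: 30 and 46). It gives 55.1 events at month 50, and 60 events at about month 54.2. The model therefore represents the plan well.

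**2. Planned design** (exponential EFS, 48:24, uniform accrual, no dropout). With cutoff T, hazard λ = ln 2/median and landmark t:

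P(censored event-free before t) = [exp(−λ(T − 50)) − exp(−λt)] / (50λ)

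At T = 54.2 and t = 24:
- Ibrutinib + CIT: (0.750 − 0.189)/3.466 = 0.162, times 48 = 7.8 subjects.
- CIT: (0.562 − 0.036)/6.931 = 0.076, times 24 = 1.8 subjects.
- Total: 9.6 of 72 (13%). At T = 50 the same formula gives 14.6 (20%).

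In 10,000 simulated trials cut at the 60th event, rates were as follows (ibrutinib + CIT vs CIT):

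| Rule for censored subjects | 24 months | 36 months |
|---|---|---|
| Failure | 11.6 vs 2.2% | 3.0 vs 0.3% |
| Dropped | 13.8 vs 2.4% | 3.7 vs 0.3% |
| Event-free | 28.0 vs 10.2% | 22.6 vs 8.7% |
| Kaplan-Meier | 19.0 vs 3.9% | 8.3 vs 1.5% |
| True | 18.9 vs 3.6% | 8.2 vs 0.7% |

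The three counting rules disagreed on significance at the 10% level in 41% of trials at 2 years and 42% at 3 years.

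**3. After the futility stop.** The final sample size and follow-up are not in the documents. Assume Table 11's 46 subjects as 31:15, uniform entry over 32 months, HR 0.878 (the futility boundary), and follow-up ending L months after last entry. Potential follow-up is then uniform from L to L + 32, and for landmark t:
- failure = S(t) × (L + 32 − t)/32
- unknown = ∫ S(u) du from L to t, divided by 32
- event-free = failure + unknown
- dropped = failure/(1 − unknown)

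There are two control curves: (a) exponential with median 5 months; (b) S(t) = 0.1 + 0.9 exp(−t ln 3/12). Curve (b) gives the 40% and 20% at 1 and 2 years in Protocol 1.1, and 13.3% at 3 years.

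Worked case, (b), ibrutinib, t = 24, L = 6: S(24) = 0.20^0.878 = 0.2434. Failure = 0.2434 × 14/32 = 0.1065. Unknown = 0.2251. Event-free = 0.3316. Dropped = 0.1065/0.7749 = 0.137.

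| Setting | Unknown | Ibrutinib + CIT: failure / dropped / event-free (true) | CIT (true) |
|---|---|---|---|
| (a) 24 months, L = 6 | 10% | 2.4 / 2.6 / 13.3% (5.4%) | 1.6 / 1.7 / 10.6% (3.6%) |
| (b) 24 months, L = 6 | 22% | 10.6 / 13.7 / 33.2% (24.3%) | 8.8 / 10.9 / 28.7% (20.0%) |
| (b) 24 months, L = 12 | 12% | 15.2 to 27.5% (24.3%) | 12.5 to 23.1% (20.0%) |
| (b) 36 months, L = 24 | 7% | 10.7 to 18.2% (17.0%) | 8.3 to 14.4% (13.3%) |

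The 24-month difference at L = 6 is 0.8 / 0.9 / 2.8 points in (a) (true 1.8) and 1.9 / 2.8 / 4.5 in (b) (true 4.3). At HR 1.0 it is zero or close to it under every rule, but the rates still span 1.6 to 10.6% in (a) and 8.8 to 28.7% in (b).

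**4. Kaplan-Meier in the same settings.** At 24 months and L = 6, carrying the last value forward, it gives 5.8 vs 4.6% in (a) and 24.5 vs 20.2% in (b) (3,000 trials each). If events are dated exactly but censoring is set back to the last scheduled scan (6, 12, 24, 36 months), it is low: 3.8 vs 3.0% in (a) and 19.0 vs 15.6% in (b). These are still closer to the truth than any counting rule.

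**The case against.** - **Crude is not the SAP's word here.** SAP 5.5.3 uses it for ORR, and 5.4.4 does not, so a chi-square comparison of Kaplan-Meier rates is not strictly excluded. But a proportion of subjects tested by chi-square in ITT is ordinarily a 2×2 table, and nothing in 5.4.4 or Table 3 links it to the Kaplan-Meier curve.
- **The planned-design figures are superseded.** With enrollment stopped and about 46 subjects, 60 events cannot occur. This stands: section 2 of the working shows the flaw in the method as written, not the coming analysis.
- **The live figures rest on assumed follow-up.** This also stands. Table 11's 46 subjects at 32 months is an HR 0.5 figure; at HR 0.878 the model expects 34.9 events in (a) and 26.8 in (b), against 31 reported. The two settings bracket the report but do not fit it.
- **Kaplan-Meier is not always the closest.** With scan-date censoring, its error in (b) at 24 months and L = 12 (about −3 points) equals that of the event-free rule (about +3). At 36 months and L = 24 it gives 15.3 vs 11.9% (true 17.0 vs 13.3%), and the event-free rule is nearer. Reporting only estimable results is also selective: in (b) at 36 months and L = 6, control averages 7.6% where estimable (true 13.3%), with 63% of trials not estimable. These points limit the precision of the remedy; they do not validate a chi-square on unobserved statuses.
- **The stakes are modest.** The endpoint is outside the ordered testing list in SAP 5.2, the Kaplan-Meier curve is already planned, and type I error is not inflated: with equal hazards, the 2-year test rejected in 3% to 10.5% of trials at a nominal 10%. All true, and they cap the severity.

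**Conclusion.** The concern holds. The method in SAP 5.4.4 and Table 3 is not valid for subjects censored before the landmark, and no rule in the documents repairs it. At 24 months with 6 months of follow-up after last entry, the ibrutinib rate spans a factor of about 3 in (b) (33.2/10.6) to more than 5 in (a) (13.3/2.4), depending on the unstated rule. In (b) the factor falls to about 1.8 with 12 months (27.5/15.2). Without dropout, the problem disappears at 24 months with 24 months of follow-up after last entry, and at 36 months with 36.

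That limit is not quite clean. The 24- and 36-month scans are timed from Cycle 1 Day 1 with a 7-day window, while EFS runs from randomization. A fully followed subject scanned slightly early can therefore be censored just short of the landmark, and no scheduled scan follows the one at 36 months.

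The effect is on the reported rates. After the stop the between-arm difference moves little, and the primary conclusion does not change. It should be fixed, as a secondary-endpoint matter.

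**What to change.** In SAP 5.4.4 and Table 3, replace the proportions and chi-square with Kaplan-Meier EFS estimates at 24 and 36 months by arm, for IRC and investigator assessment. Give 90% confidence intervals where defined, the number at risk, and the number censored before each time. Report an estimate as not estimable when the last observation in an arm is censored before the landmark; do not carry the last value forward. Leave the between-arm test to the log-rank test in SAP 5.4.2. Record in SAP Section 9 that the endpoint is summarized, since Protocol 11.3.2 would only list it.

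The cost is wording only, because the curve is already planned. The landmark p-value is lost, and some estimates may not be available. Not-estimable rates (ibrutinib/control) at 36 months are 40%/30% of trials in (a) and 59%/62% in (b) with 6 months of follow-up after last entry, falling to 15%/7% and 2%/14% with 24 months. At 24 months with 6 months of follow-up they are 15%/19% in (a) and 2%/13% in (b). If the sponsor wants a landmark comparison, a difference in Kaplan-Meier estimates with Greenwood variance would serve in place of the chi-square.

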5.4.5. Subgroup Analysis of EFS

Subgroup analysis will be performed for the selected potential prognostic variables (as listed in Section 2.4) to assess the consistency and robustness of the treatment benefit for EFS. A non-stratified log-rank test analysis method for EFS will be used for each of the subgroup analyses. Median EFS with 90% CI, and hazard ratio between the 2 treatment groups within each subgroup and their 90% CI will be calculated using non-stratified Cox regression model. Subgroup analysis will be presented graphically in a forest plot.

5.5. Secondary Endpoints

5.5.1. Overall Survival

Overall survival is defined as the duration from the date of enrollment (in Part 1) or randomization (in Part 2) to the date of the subject's death. Overall survival will be analyzed using the non-stratified log-rank test for treatment comparison in Part 2. Survival time of living subjects will be censored on the last date a subject is known to be alive or lost to follow-up.

The overall survival distribution and median overall survival with its 90% confidence interval will be estimated using the Kaplan-Meier product-limit method. The hazard ratio for ibrutinib+CIT relative to CIT alone and its associated 90% confidence interval will be calculated based on the non-stratified Cox proportional hazards model.

The same subgroup analysis used for EFS will be performed for OS if the number of events within each subgroup is sufficient.

5.5.2. Sensitivity Analysis of Overall Survival

Sensitivity analysis will be performed for OS where censoring occurs at subsequent antilymphoma therapy or conditioning regimen for stem cell transplantation.

5.5.3. Overall Response Rate

Overall response rate is defined as the proportion of subjects achieving a best overall response of either CR (including CR_b and CR_u) or PR as evaluated by IRC.

All randomized subjects with a measurable disease at baseline will be included in this analysis. Subjects with missing post-randomization data are considered non-responders.

Overall response rate will be estimated according to the crude proportion of confirmed responders (PR or better) based on the best overall response and summarized by treatment arm. Overall response rate will be compared between treatment arms using a 2-sided chi-square test at the 10% level of significance and 90% confidence intervals.

The relative risk (ibrutinib + CIT vs. CIT) will be reported along with the associated 95% confidence interval. Statistical inference will be evaluated using Chi-square statistic.

For overall response rate based on investigators' assessment, same analysis methods used for IRC reported overall response will be used.

Subgroup analysis for ORR may be performed if the number of responders within each subgroup is sufficient.

For enrolled subjects in Part 1, IRC and investigator response will be listed.

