
 Evaluate the safety and tolerability of ibrutinib in combination with RICE or RVICI background therapy in pediatric subjects and young adults with B-cell malignancies Determine the ORR Evaluate tumor volume reduction at Day 14 Determine the number and proportion of subjects who proceed to stem cell transplantation Evaluate the time to response Measure the duration of response Evaluate long-term survival (EFS at 2 and 3 years) Evaluate overall survival Assess disease-specific biomarkers Assess the pharmacodynamic response, if deemed appropriate based on Part 1 results Assess the population pharmacokinetics of ibrutinib in pediatric subjects and young adults Acceptability and palatability assessment of all ibrutinib formulations 	
 Safety parameters, including gastrointestinal effects, immune function, intensified cardiac monitoring (in particular, after previous anthracycline exposure) The proportion of subjects who achieve CR, (including CR_b and CR_u) and PR Percent decrease in the sum of the products of the lesion diameters at Day 14 Number and proportion of subjects who proceed to stem cell transplantation The time interval from the first dose of ibrutinib to the first documented response for those subjects who respond Duration calculated from the date of initial documentation of a response (CR or PR) to the date of first documented evidence of PD or death Proportion of subjects with EFS at 2 and 3 years The duration from the date of randomization to the date of the subject's death Phosphor-BTK, as well as SYK, STAT3, caspase-3, BCL-xL, and cIAP1 expression at baseline and during treatment BCR/CD79B, CARD11, and MYD mutations c-MYC, immunoglobulin, and T-cell receptor gene rearrangements at baseline BTK occupancy Population pharmacokinetic parameters and derived systemic exposure to ibrutinib such as AUC Relationship between pharmacokinetic parameters and age or measure of body size Visual analog scale score for palatability
Exploratory	

 Evaluate other response biomarkers Explore the exposure-response relationships 	
 Other biomarkers, as applicable Potential relationships between systemic exposure and response

Refer to Section 9, Study Evaluations, for evaluations related to endpoints.

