At the time of PD or if residual disease is present upon completion of 3 cycles, the subject is considered eligible to receive subsequent antilymphoma therapy. Subsequent antilymphoma therapy will be recorded in the electronic CRF. Subjects with residual disease who receive subsequent antilymphoma therapy will be followed until PD, end of the study, or death. Investigators should maintain adequate contact with the subject to obtain follow-up information on safety and survival status. Where allowed by local law, public records may be used to document death. Any new malignancy reported during the posttreatment follow-up phase will be recorded in the CRF (Section 12.3.4).

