9.2.5. Efficacy Criteria

All efficacy assessments must continue until disease progression (even if subsequent antilymphoma therapy is started), withdrawal of consent from study participation, or clinical cutoff for the primary analysis. The Sponsor Medical Monitor is to be notified within 24 hours for subjects who have disease progression and central assessment will ensue. Imaging, bone marrow assessments and CSF evaluations are required at Screening, Cycle 3 Day 1, and at End of Treatment. CSF evaluation is also required at Cycle 2 Day 1, but bone marrow is only

required at this time point if clinically indicated. Subjects without nodal disease (ie, subjects with bone marrow only disease) only require imaging at Screening. Imaging evaluations performed on Cycle 1 Day 14 are exploratory; if PD is indicated based on these scans, investigator discretion should be used to determine if the clinical evaluation is consistent with progressive disease. If not, the subject may continue with study treatment until confirmation of PD or the subject meets other criteria for withdrawal.

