11.1. Subject Information

The intent-to-treat (ITT) Population will consist of all randomized subjects where subjects will be analyzed based on randomization, regardless of study drug received. The ITT population will be used for all efficacy analyses. The primary efficacy analysis is based on the ITT population for data collected in the Part 2. Efficacy for Part 1 will be provided as a secondary endpoint for Part 1.

The Safety population will consist of all subjects who received at least 1 dose of treatment. The safety population will be used for all safety analyses and subjects will be analyzed based on actual study drug received.

Summaries (demographics and baseline characteristics, safety) will be presented for Part 1 and Part 2 of the study. Analyses of disposition, demographic, baseline disease characteristics, and prior and concomitant therapy will be conducted on the ITT population. Analyses on treatment compliance and extent of exposure will be conducted on the Safety population. No statistical testing is planned.

Unless otherwise specified, all continuous endpoints will be summarized using descriptive statistics, which will include the number of subjects with a valid measurement (n), mean, standard deviation, median, minimum, and maximum. All categorical endpoints will be summarized using frequencies and percentages. Percentages will be calculated by dividing the number of subjects with the characteristic of interest by the number of subjects in the analysis population or the evaluable population.

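### ORR takes the best overall response with no cutoff at subsequent therapy, so a non-progressing non-responder can become a responder on a later regimen

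*SAP*

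**What the plan says.** The protocol endpoint (2.1.2) is "The proportion of subjects who achieve CR, (including CR_b and CR_u) and PR", with no time limit. SAP 5.5.3 is fuller and makes the IRC the assessor, but adds no limit either: "Overall response rate is defined as the proportion of subjects achieving a best overall response of either CR (including CR_b and CR_u) or PR". The estimator is "Overall response rate will be estimated according to the crude proportion of confirmed responders (PR or better) based on the best overall response", and the test is given as "Overall response rate will be compared between treatment arms using a 2-sided chi-square test at the 10% level of significance". SAP Table 3 names the same test and sets no window.

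Three protocol sections decide which assessments exist. Under 8.4 and 9.1.4, residual disease after 3 cycles is enough for a subject to receive subsequent antilymphoma therapy; PD is not required. Under 9.2.5, efficacy assessments go on until progression, "even if subsequent antilymphoma therapy is started". Under 9.1.4, "Subjects with residual disease who receive subsequent antilymphoma therapy will be followed until PD, end of the study, or death".

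The SAP does have rules for subsequent therapy elsewhere: in the EFS sensitivity analyses (5.4.3), the OS sensitivity analysis (5.5.2) and the treatment-emergent period (6.1.1). It has none for ORR. In the fixed testing order of SAP 5.2, ORR is the first secondary endpoint.

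**The concern.** ORR should describe what the randomized regimen achieved. As written, it describes the best status a subject reaches before progression on any treatment.

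This puts ORR at odds with the primary endpoint. SAP 5.4.1 counts the absence of CR or PR after 3 cycles as an EFS event. A subject who fails that test without PD, starts another regimen and reaches CR on a later scan is a failure for EFS and a success for ORR. The SAP does not reconcile the two.

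Similar numbers of such responses in both arms would dilute a true difference. If switching differs by arm, it could shift the comparison in either direction. Under SAP 5.5.5, time to response ends, and duration of response begins, at the first documented response, so both could take their date from a regimen the trial does not test.

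**Working it through.** **1. Can the case arise?** Follow a subject with minor or no response and no PD after cycle 3.

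- EFS: an event, for lack of CR or PR (SAP 5.4.1).
- New therapy: permitted (Protocol 8.4, 9.1.4).
- Later scans: still required (Protocol 9.2.5). Protocol Table 4 schedules CT/MRI at 6, 12, 24 and 36 months after Cycle 1 Day 1.
- ORR: a CR or PR on one of those scans meets the SAP 5.5.3 definition for the randomized arm.

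Nothing in the SAP interrupts this chain.

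**2. The plan's own figure.** The documents state no expected rate or power for ORR. The only stated power is for EFS: at least 80% with 60 events, hazard ratio 0.5, 2:1 allocation and 1-sided alpha 0.05. Check: √(60 × 2/9) × ln 2 − 1.645 = 2.531 − 1.645 = 0.886, and Φ(0.886) = 0.81. It reproduces and does not depend on how ORR is defined.

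**3. Weight of one response at the planned 48 versus 24.** CIT alone: 1/24 = 4.2 points. Ibrutinib plus CIT: 1/48 = 2.1 points.

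**4. Dilution.** Assumptions, none of them in the documents: ORR with the cutoff is 80% (ibrutinib) versus 60% (CIT); a share f of non-responders switch without PD; a share s of those switchers respond. The counted rate is then p + (1 − p) × f × s. Power is for the uncorrected chi-square test, 2-sided 10%, by exact binomial enumeration; it is the probability of rejecting in favour of ibrutinib.

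| f | s | CIT | Ibrutinib | Power |
|---|---|---|---|---|
| 0 | – | 60.0% | 80.0% | 57% |
| 1/3 | 10% | 61.3% | 80.7% | 56% |
| 1/3 | 20% | 62.7% | 81.3% | 54% |
| 1/3 | 30% | 64.0% | 82.0% | 52% |
| 1/2 | 10% | 62.0% | 81.0% | 55% |
| 1/2 | 20% | 64.0% | 82.0% | 52% |
| 1/2 | 30% | 66.0% | 83.0% | 49% |

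Example, last row: 0.60 + 0.40 × 0.5 × 0.3 = 0.66, and 0.80 + 0.20 × 0.5 × 0.3 = 0.83.

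**5. Bias if switching differs by arm.** Assume no true difference, 60% in each arm. The 60% matches the response rate that Protocol 1.2 reports for RICE. The test then rejects 5.5% of the time in favour of ibrutinib and 5.3% in favour of CIT. Now let 20% of one whole arm and 10% of the other be non-progressing switchers, half of whom respond (again assumptions). The counted rates become 0.60 + 0.20 × 0.5 = 70% and 0.60 + 0.10 × 0.5 = 65%.

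- More switching on CIT: 2.1% in favour of ibrutinib, 11.3% in favour of CIT.
- More switching on ibrutinib: 12.2% in favour of ibrutinib, 2.0% in favour of CIT.

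**The case against.** The strongest reply is that the route is narrow, and that stands. Required assessments stop at PD, so responses to treatment given after progression should not normally enter. Under Protocol 9.1.3, subjects in CR after 2 cycles may go to transplant, but they are already responders. What remains is essentially minor or no response without PD, followed by new therapy and a CR or PR on a sparse follow-up scan. A reader might infer that salvage and transplant responses in general inflate ORR; the documents do not support that. Nor do they support applying a later response rate to every non-responder, since some have progressed or died. Protocol 1.2 gives a median survival of 2.5 months for subjects who failed RICE.

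The separate IRC charter may also set a cutoff. It is not available here, and SAP 5.5.3 does not point to it for one. Hence these responses can count; it is not shown that they do.

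The practical stakes are limited too. ORR is formally tested only if the primary hypothesis is rejected. Protocol 11.9.1 reports that the futility boundary was reached at 31 events and that enrollment stopped, so 48 versus 24 is the planned size. SAP 5.4.3 cross-tabulates IRC and investigator response after 3 cycles, so on-treatment response is at least visible. None of this supplies the missing rule.

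Two further inferences from the same SAP section fail:

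- The reference to confirmed responders might suggest that no confirming assessment exists. Footnotes to Protocol Tables 1 to 4 allow additional or repeat assessments to confirm response. What is missing is a stated rule.
- The protocol says "The ITT population will be used for all efficacy analyses" and the SAP says "All randomized subjects with a measurable disease at baseline will be included in this analysis", which might suggest that subjects with only marrow or CSF disease are lost. Protocol 9.2.5.1 accepts CSF blasts, or more than 25% marrow blasts, as measurable disease in the absence of nodal disease. SAP 5.5.3 already counts missing post-randomization data as non-response. A change to the all-ITT set is not needed for this point.

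**Conclusion.** The point holds in a limited form. Read literally, SAP 5.5.3 lets a subject who is an EFS failure for lack of response be counted as an ORR responder because of a later regimen. The date used for time to response and duration of response has the same gap.

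The documents do not give the size. The firm figures are 4.2 points per such response on CIT alone and 2.1 points on ibrutinib, at the planned sample size. Power of about 49-56% against 57%, and the shifts in rejection rate under unequal switching, rest on assumed switching and response rates. The direction of any bias is unknown. The EFS analysis, its power and its boundaries are unaffected.

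**What to change.** In SAP 5.5.3, restrict best overall response to IRC assessments up to the earliest of PD, start of subsequent antilymphoma therapy, or start of a transplant conditioning regimen. In SAP 5.5.5, apply the same cutoff to the response date that ends time to response and starts duration of response. Keep the unrestricted ORR as a sensitivity analysis.

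The cost is SAP wording and a small programming change. Protocol 8.4 already has the start date of subsequent therapy recorded in the electronic CRF. The downside is that a few late responses drop out of the main analysis, so ORR may be slightly lower.
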